## SUPPLEMENTAL TABLES

**Table E1. Composition of the study fluids.**

	Sodium	Potassium	Calcium	Magnesium	Chloride	Acetate	Lactate	Gluconate	Osmolarity
Plasma	135–145	4.5–5.0	2.2–2.6	0.8–1.0	94–111		1–2		275–295
0.9% saline	154				154				308
Lactated Ringer's	130	4.0	2.7		109		28		273
Plasma-Lyte A®	140	5.0		3.0	98	27		23	294

All values are in mEq/L except calculated osmolarity, which is in mOsm/L. 0.9% saline is “Sodium Chloride Injection, USP”, Lactated Ringer’s is “Lactated Ringer’s Injection, USP”, and Plasma-Lyte A® is “Multiple Electrolyte Injection, Type 1, USP”, all from Baxter Healthcare Corporation in Deerfield, IL, USA.

**Table E2. Elixhauser comorbidity index.**

	Saline	Balanced
Comorbidity, No. (%)	(n = )	(n = )
Congestive heart failure	--	--
Cardiac arrhythmias	--	--
Valvular disease	--	--
Pulmonary circulation disorders	--	--
Hypertension, uncomplicated	--	--
Hypertension, complicated	--	--
Paralysis	--	--
Other neurological disorders	--	--
Chronic pulmonary disease	--	--
Diabetes, uncomplicated	--	--
Diabetes, complicated	--	--
Hypothyroidism	--	--
Renal failure	--	--
Liver disease	--	--
Peptic ulcer disease excluding bleeding	--	--
Acquired immunodeficiency syndrome	--	--
Lymphoma	--	--
Metastatic cancer	--	--
Solid tumor without metastasis	--	--
Rheumatoid arthritis / collagen vascular disease	--	--
Coagulopathy	--	--
Obesity	--	--
Weight loss	--	--
Fluid and electrolyte disorders	--	--
Blood loss anemia	--	--
Deficiency anemias	--	--
Alcohol abuse	--	--
Drug abuse	--	--
Psychoses	--	--
Depression	--	--

**Table E3. Intravenous fluids and blood products.**

	Saline	Balanced Crystalloid	
	(n = )	(n = )	P value
0.9% sodium chloride, median [IQR]; mean ± SD, mL			
Prior to enrollment on Day 0	--	--	--
Cumulative volume from enrollment through day 3	--	--	--
Cumulative volume from enrollment through day 7	--	--	--
Cumulative volume from enrollment through day 14	--	--	--
Cumulative volume from enrollment through day 30	--	--	--
Cumulative volume from enrollment through ICU transfer	--	--	--
Prior to an ICU crossover in fluid assignment	--	--	--
After an ICU crossover in fluid assignment	--	--	--
Cumulative volume from ICU transfer to hospital discharge	--	--	--
Lactated Ringer's, median [IQR]; mean ± SD, mL			
Prior to enrollment on Day 0	--	--	--
Cumulative volume from enrollment through day 3	--	--	--
Cumulative volume from enrollment through day 7	--	--	--
Cumulative volume from enrollment through day 14	--	--	--
Cumulative volume from enrollment through day 30	--	--	--
Cumulative volume from enrollment through ICU transfer	--	--	--
Cumulative volume from ICU transfer to hospital discharge	--	--	--
Plasma-Lyte A®, median [IQR]; mean ± SD, mL			
Prior to enrollment on Day 0	--	--	--
Cumulative volume from enrollment through day 3	--	--	--
Cumulative volume from enrollment through day 7	--	--	--
Cumulative volume from enrollment through day 14	--	--	--
Cumulative volume from enrollment through day 30	--	--	--
Cumulative volume from enrollment through ICU transfer	--	--	--
Cumulative volume from ICU transfer to hospital discharge	--	--	--
Balanced crystalloid, median [IQR]; mean ± SD, mL			
Prior to enrollment on Day 0	--	--	--
Cumulative volume from enrollment through day 3	--	--	--
Cumulative volume from enrollment through day 7	--	--	--
Cumulative volume from enrollment through day 14	--	--	--
Cumulative volume from enrollment through day 30	--	--	--
Cumulative volume from enrollment through ICU transfer	--	--	--
Prior to an ICU crossover in fluid assignment	--	--	--
After an ICU crossover in fluid assignment	--	--	--
Cumulative volume from ICU transfer to hospital discharge	--	--	--
"Hypotonic" crystalloid, median [IQR]; mean ± SD, mL			
Prior to enrollment on Day 0	--	--	--
Cumulative volume from enrollment through day 3	--	--	--
Cumulative volume from enrollment through day 7	--	--	--

Cumulative volume from enrollment through day 14	--	--	--
Cumulative volume from enrollment through day 30	--	--	--
Cumulative volume from enrollment through ICU transfer	--	--	--
Cumulative volume from ICU transfer to hospital discharge	--	--	--
Human albumin solutions, median [IQR]; mean $\pm$ SD, mL			
Prior to enrollment on Day 0	--	--	--
Cumulative volume from enrollment through day 3	--	--	--
Cumulative volume from enrollment through day 7	--	--	--
Cumulative volume from enrollment through day 14	--	--	--
Cumulative volume from enrollment through day 30	--	--	--
Cumulative volume from enrollment through ICU transfer	--	--	--
Cumulative volume from ICU transfer to hospital discharge	--	--	--
Blood products, median [IQR]; mean $\pm$ SD, mL			
Prior to enrollment on Day 0	--	--	--
Cumulative volume from enrollment through day 3	--	--	--
Cumulative volume from enrollment through day 7	--	--	--
Cumulative volume from enrollment through day 14	--	--	--
Cumulative volume from enrollment through day 30	--	--	--
Cumulative volume from enrollment through ICU transfer	--	--	--
Cumulative volume from ICU transfer to hospital discharge	--	--	--

**Table E4. Serum laboratory values.**

Laboratory value	Saline (n = )	Balanced (n = )	P value
Serum sodium, mmol/L			
Highest between enrollment and day 30, median [IQR]	--	--	--
Lowest between enrollment and day 30, median [IQR]	--	--	--
>145 between enrollment and day 30, No. (%)	--	--	--
< 135 between enrollment and day 30, No. (%)	--	--	--
Serum potassium, mmol/L			
Highest between enrollment and day 30, median [IQR]	--	--	--
Lowest between enrollment and day 30, median [IQR]	--	--	--
> 5.0 between enrollment and day 30, No. (%)	--	--	--
< 3.0 between enrollment and day 30, No. (%)	--	--	--
Serum chloride, mmol/L			
Highest between enrollment and day 30, median [IQR]	--	--	--
Lowest between enrollment and day 30, median [IQR]	--	--	--
> 110 between enrollment and day 30, No. (%)	--	--	--
< 90 between enrollment and day 30, No. (%)	--	--	--
Serum bicarbonate, mmol/L			
Highest between enrollment and day 30, median [IQR]	--	--	--
Lowest between enrollment and day 30, median [IQR]	--	--	--
> 30 between enrollment and day 30, No. (%)	--	--	--
< 20 between enrollment and day 30, No. (%)	--	--	--

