### **2.4 Chloride and Renal Function**

Animal studies have suggested a role for chloride in regulating renal blood flow. A study of denervated dog kidneys infused with chloride-solutions showed vasoconstriction only in the renal vessels associated with decreased glomerular filtration. Proposed mechanisms for chloride-mediated vasoconstriction include tubuloglomerular feedback in which chloride detection in the distal tubule triggers mesangial contraction and decreased filtration, thromboxane-mediated vasoconstriction, and chloride-mediated potentiation of angiotensin II response in the renal vasculature.

Studies on human volunteers have shown decreased renal blood flow, increased time to micturition, and decreased diuresis and natiuresis in patients treated with fluids with higher chloride content. Studies of patients undergoing surgery have linked higher chloride solutions to decreased urine output and increased urinary markers of kidney injury. A randomized controlled trial of lactated Ringer's versus saline in patients undergoing renal transplantation was stopped early for a higher incidence of hyperkalemia and metabolic acidosis in the saline group.

Recently, a prospective, open-label, before-after study of over 1400 patients in a single intensive care unit transitioning from use of higher to lower chloride solutions

Principal Investigators: [name], [name]

Version Date: 6/15/17

Study Title: Isotonic Solutions and Major Adverse Renal Events Trial (SMART)

Institution/Hospital: Vanderbilt University Medical Center

demonstrated an association between higher chloride fluid and the development of acute kidney injury and use of renal replacement therapy.

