#### Order Entry:

For the duration of the study, when a provider begins an order for the administration of any isotonic crystalloid in the electronic order entry system an "Isotonic Fluid Wizard" will: 1) Inform the provider of the study, 2) Solicit the presence of contraindications to the assigned study fluid, and 3) If contraindications are not present, guide the provider to order the assigned study fluid. The manner in which fluid orders can be customized with regard to total volume, rate, electrolyte and dextrose content will not be affected by the advisor.

There are no established contraindications to the choice of 0.9% saline once the decision has been made to administer an isotonic crystalloid. **Because of the marginally higher potassium content of Plasma-Lyte A® and lactated Ringer's, patients being**

Principal Investigators: [name], [name]

Version Date: 6/15/17

Study Title: Isotonic Solutions and Major Adverse Renal Events Trial (SMART)

Institution/Hospital: Vanderbilt University Medical Center

**treated for hyperkalemia will be allowed to receive saline regardless of study group. Because of the concern for the use of relatively hypotonic solutions in patients with elevated intracranial pressure, these patients will also be allowed to receive saline regardless of study group.** While there may be patients in whom treating providers prefer not to administer Ca2+ or lactate (as in lactated Ringer's) or magnesium (as in Plasma-Lyte A®), because an alternative balanced solution would be available without these electrolytes, saline would not be allowed for these indications in those assigned to the balanced crystalloid group. Instead, the provider would have the option of choosing the other balanced crystalloid (i.e. choose Plasma-Lyte A® if worried about administering Ca2+ or lactate and choose lactated Ringer's if worried about administering magnesium or acetate).

The non-assigned crystalloid will also be made available via the pharmacy if a formal statement is submitted that the attending physician feels the non-assigned crystalloid is required for the safe treatment of a specific patient.

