### **10.0 Adverse Events:**

An adverse event is defined as any untoward medical occurrence in a patient or clinical investigation participant administered an intervention that does not necessarily have to have a causal relationship with this treatment. An adverse event therefore can be any unfavorable and unintended sign, symptom, or disease temporally associated with the

Principal Investigators: [name], [name]

Version Date: 6/15/17

Study Title: Isotonic Solutions and Major Adverse Renal Events Trial (SMART)

Institution/Hospital: Vanderbilt University Medical Center

use of an intervention, whether or not the incident is considered to be related to the intervention.

A serious adverse event (SAE) is defined as any untoward medical occurrence that meets any of the following criteria:

- a. Results in death
- b. Is life-threatening (defined as an event in which the participant was at risk of death at the time of the event and NOT an event that hypothetically might have caused death if it would have been more severe)
- c. Requires inpatient hospitalization
- d. Prolongs an existing hospitalization
- e. Results in persistent or significant disability or incapacity
- f. Results in a congenital anomaly or birth defect
- g. Important medical event that requires an intervention to prevent any of a-f above.

The Principal Investigator will be responsible for overseeing the safety of this trial on a daily basis. He will be available at any time for questions from the bedside nurses, who will also be monitoring the patients continuously for adverse events and serious adverse events. Serious and unexpected adverse events associated with study interventions will be recorded in a case report form in the study record and reported to the IRB within 10 business days. As critically ill adults receiving intravenous crystalloid administration are known to be at risk for numerous adverse outcomes including Major Adverse Kidney Events, death, new RRT, persistent renal dysfunction, acute kidney injury, receipt of mechanical ventilation, receipt of vasopressors, hyponatremia, hypernatremia, hypokalemia, hyperkalemia, hypochloremia, hyperchloremia, acidosis, and alkalosis, these events will be systematically recorded as study outcomes. These study outcomes will not be individually reported to the IRB as adverse events, unless the investigators or clinical team believe the event was related to the study intervention.

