## Additional Secondary Analyses

We will perform the following additional secondary analyses:

- (1) Comparison of secondary outcomes between study groups.
- (2) Effect modification by severity of illness and pre-specified subgroups. Using generalized linear mixed effects modeling, we will examine the interaction between crystalloid assignment and the following baseline variables with respect to the primary outcome of MAKE30 in the intention-to-treat population:

- a. Source of admission to the ICU (Emergency department, Operating room, Transfer from another hospital, Hospital ward, Other)
- b. Study ICU (Medical, Surgical, Cardiac, Neurological, Trauma). [Because cluster cannot be treated as a random effect for this subgroup, we will use logistic regression modeling]
- c. Sepsis or septic shock (Yes, No)
- d. Traumatic brain injury (Yes, No)
- e. Receipt of mechanical ventilation (Yes, No)
- f. Receipt of vasopressors (Yes, No)
- g. Category of renal dysfunction at the time of enrollment (No renal dysfunction, Acute kidney injury, Chronic kidney disease, End-stage renal disease receiving RRT)
- h. Risk of in-hospital mortality as predicted by baseline University HealthSystem Consortium expected in-hospital mortality (continuous variable ranging 0.0 to 1.0)

(3) Sensitivity analysis excluding patients admitted in the week prior to a crossover ('washout'). We will repeat the primary analysis comparing MAKE30 between study groups in the intention to treat population excluding those admitted in the 7 days prior to a crossover in ICU crystalloid assignment (simulating a "washout" period). Prior data from the study ICUs suggests that less than 10% of patients remain in the ICU for longer than 7 days[14]. Excluding those admitted within 7 days of a crossover in ICU crystalloid assignment will allow use of a baseline factor to exclude the majority of patients who would go on to experience a crossover in crystalloid assignment due to the study design.

(4) Sensitivity analysis excluding patients who were transferred between ICUs or remained in the ICU through a crossover ('per protocol'). We will repeat the primary analysis comparing MAKE30 between study groups in the intention to treat population excluding those who remained in the intensive care unit through a crossover in crystalloid assignment or were transferred between study ICUs.

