**Table E5. Indications for new renal replacement therapy.**

Indication, No. (%)	Saline (n = )	Balanced (n = )	P Value
Oliguria	--	--	--
Hyperkalemia with serum potassium > 6.5 mEq/L	--	--	--
Acidemia with pH < 7.20	--	--	--
Blood urea nitrogen > 70 mg/dL	--	--	--
Serum creatinine > 3.39 mg/dL	--	--	--
Organ edema	--	--	--
Other renal failure–related indication	--	--	--
Other non–renal failure–related indication	--	--	--

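### No count of severe hyperkalemia is planned for all patients: Table E4 counts any potassium above 5.0, and the SAP's 6.5 cut is tabulated only as an indication for new RRT

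*Combined protocol and SAP*

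**What the plan says.** **Why potassium matters to the plan.** The final protocol (15 June 2017), Section 8.1, Order Entry, gives a reason for its exception: "Because of the marginally higher potassium content of Plasma-Lyte A" and lactated Ringer's, patients under treatment for hyperkalemia may receive saline in either group. The SAP (Study Interventions) lists hyperkalemia as one of two accepted relative contraindications and leaves its severity to the clinician. Protocol Section 2.4 points the other way, citing a renal-transplant trial that was "stopped early for a higher incidence of hyperkalemia and metabolic acidosis in the saline group".

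**How hyperkalemia is reported.** Section 10.0 places it among the events recorded systematically as study outcomes, and limits individual reporting to events thought to be connected with the intervention: "These study outcomes will not be individually reported to the IRB as adverse events, unless the investigators or clinical team believe the event was related".

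**What is tabulated by group.**
- Table E4 has four potassium rows: highest and lowest value as median and IQR, a high count ("> 5.0 between enrollment and day 30, No". (%)) and a low count ("< 3.0 between enrollment and day 30, No". (%)).
- Table E1 gives plasma potassium as 4.5-5.0 mEq/L. For potassium, mEq/L and mmol/L are the same number.
- Table E5 has the row "Hyperkalemia with serum potassium > 6.5 mEq/L". Protocol Section 8.4.2 collects these indications only in patients receiving new RRT.
- Serial potassium is a secondary outcome and is plotted over time by group (SAP, Secondary Outcomes and Presentation of the Results).
- Renal-dysfunction categories appear in Additional Secondary Analyses (2)(g), where effect modification is examined "with respect to the primary outcome of MAKE30 in the intention-to-treat population". Potassium is not reported by these categories.

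**The concern.** Because Section 10.0 treats hyperkalemia as a study outcome, the planned tables are where a between-group difference has to show. The one all-patient count of high potassium starts where the SAP's plasma range ends. It adds a value just above 5.0 to a value above 6.5 as if they were the same event.

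The severe cut in Table E5 leaves out severe hyperkalemia managed without RRT. It also leaves out patients on RRT before enrollment, who by definition cannot have new RRT.

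At stake is whether the trial can describe a risk its own protocol names, in either direction. The SAP Discussion expects the result to inform the preferred crystalloid for most acutely ill patients. Under its closing section, any analysis not listed is post hoc.

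**Working it through.** **Inputs.** Enrollment of 14,000, taken as 7,000 per group; two-sided alpha of 0.05 (SAP, Power Calculation and Statistical Analysis Principles). The documents give no potassium frequencies. The rates in steps 2 and 3 are assumptions: any value above 5.0 in 15-35% of patients, any value above 6.5 in 1.0% against 1.5% or 2.0%. Patients are treated as independent.

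**Formula.** SE = √{[p₀(1−p₀) + p₁(1−p₁)]/n}; z = |p₁−p₀|/SE; power = Φ(z−1.96) + Φ(−z−1.96).

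**1. The plan's own figure.** MAKE30 15.0% against 13.1%, n = 7,000: SE = √[(0.1275 + 0.1138)/7,000] = 0.00587, z = 3.24, power 89.9%. This reproduces the stated 90%. It checks the method and says nothing about potassium.

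**2. Severe row, 1.0% against 1.5%** (70 against 105 patients). SE = √[(0.0099 + 0.0148)/7,000] = 0.00188, z = 2.66, power 75.9%.

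**3. The same 35 extra patients on the 5.0 row.** The best case for that row is that every one of them would otherwise have stayed at or below 5.0, so that its percentage rises by the full 0.5 points. At a base of 25%: SE = √[(0.1875 + 0.1900)/7,000] = 0.00734, z = 0.68, power 10.5%.

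| Severe rates | Power, row above 6.5 | Power, row above 5.0 at base 15% / 25% / 35% |
|---|---|---|
| 1.0% v 1.5% | 75.9% | 13.0% / 10.5% / 9.5% |
| 1.0% v 2.0% | 99.8% | 37.3% / 27.4% / 23.5% |

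If the extra patients would have exceeded 5.0 anyway, the count does not move and the row rejects at its 5% error rate only. That last step needs no assumed rate.

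The protocol's later enrollment estimate (15,000 to 16,500) changes little. At 7,500 per group, 1.0% against 1.5% has 78.7% power on the severe row and 13.4% on the 5.0 row at base 15%.

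**4. Do the other potassium outputs fill the gap?** A group of 7,000 peak values was simulated with 19.1% above 5.0. Then 70 patients (1%) were moved from the 5.0-6.5 band to 6.8.
- The quartiles stayed at 4.15, 4.50 and 4.88, and the share above 5.0 stayed at 19.1%. The share above 6.5 rose from 0.2% to 1.2%.
- The mean peak moves by at most 0.01 × (6.8 − 5.0) = 0.018 mmol/L, so a group curve would barely move.
- A rank-sum test on the peak is also weak here. Patients already in the top 19% can gain at most 0.19 in rank probability, so the Mann-Whitney probability shifts by at most 0.01 × 0.19 = 0.0019. Its null SE is √[14,001/(12 × 7,000²)] = 0.0049, so z is at most 0.39.

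**5. Further dilution.** The 5.0 row does not separate patients already above the cut at enrollment. It also runs to day 30, including time after ICU discharge, when the SAP says fluid is not controlled by the study.

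**The case against.** The strongest reply is that the plan covers potassium in several ways. Peak potassium is summarized, and the SAP provides for formal comparison of continuous and repeated measures. Table E5 does use a severe cut by group. Hyperkalemia believed related to the intervention stays reportable, and the DSMB can review related serious events and pause the trial. All of this stands. A reader might infer that severe hyperkalemia goes unreported, or that it has been removed from adverse-event reporting, and neither is correct. What these outputs do not provide is a severe count in all patients, and step 4 shows how little a 1% tail moves the summaries. Case-by-case reports, judged by staff who know the assignment, are no substitute for a by-group count.

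It is also fair that 5.0 fits the table's pattern. Sodium above 145 is the top of the Table E1 range and chloride above 110 lies inside it (94-111). No analyte has a severe tier. So the 5.0 row is not an error. Potassium differs in that the protocol ties it to an exception from the assigned fluid.

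A reader might also infer that an excess with balanced fluid is expected. The documents do not support that: they call the potassium difference marginal, allow saline for patients being treated for hyperkalemia, and cite a trial with more hyperkalemia under saline.

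Finally, little formal standing is lost if the analysis is done later, since additional secondary analyses are already hypothesis-generating. What prespecification adds is a cut fixed in advance and a commitment to report it.

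**Conclusion.** The point holds as a reporting gap. No all-patient count of severe hyperkalemia is planned, and a difference in either direction could be diluted in the 5.0 row or missed by the summaries. Under the assumed 1.0% against 1.5%, power is about 76% on a severe row and about 10-13% at best on the existing one. Those figures rest on assumed rates, 7,000 per group and no allowance for ICU clustering or repeat admissions, so they illustrate the loss and do not predict it. What does not depend on them is that the 5.0 count cannot change when patients already above 5.0 move higher. MAKE30 and its analysis are unaffected. This is a cheap improvement that should be made, not a flaw in the trial's main conclusion.

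**What to change.** Keep the 5.0 row. Add to Table E4 a prespecified row giving, by group, the number and percentage of all patients with any potassium above 6.5 mmol/L from enrollment through day 30. Report the between-group comparison with a 95% CI. Under the step 2 assumptions the interval would be 0.5 ± 1.96 × 0.188, or about 0.13 to 0.87 percentage points.

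Beside it, show how many patients were already above the cut at their last value before enrollment. The extracted data reach back 12 months before hospitalization, so the definition should say how recent that value must be.

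Counts by the renal categories in Additional Secondary Analyses (2)(g) should be descriptive only. Events will be sparse, and modelled odds ratios there are not needed.

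The 6.5 cut is the one the SAP already uses in Table E5. Here it serves only as a reporting threshold and changes no treatment rule.

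The cost is two table rows, a place for the interval (Table E4 now has only a P value column), a small descriptive table and a few lines of code. The potassium values are already collected under protocol Sections 8.4.1 and 8.4.2. The downside is one more hypothesis-generating safety comparison with few events.
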